9.12. Data analysis

Data in this study are analyzed as often as required to address regulatory queries, safety reporting requirements and clinical questions posed by investigators. In addition the study data are analyzed to support research projects initiated and run by investigators in partnership with Pfizer.

Detailed methodology for summary and statistical analyses of data collected in this study will be documented in a Statistical Analysis Plan (SAP) before any analysis can begin. If analyses are to be performed at several occasions (e.g. interim analyses), the respective SAPs will be dated, filed and maintained by the Sponsor and/or involved investigator(s). Results of these analyses are presented in scientific articles, posters and oral presentations at scientific meetings.

If statistical analyses on data from this study are performed by investigators, independently of Pfizer, the SAP should be approved by Pfizer Medical and a Pfizer statistician. Analysis results are reviewed by Pfizer prior to their presentation and/or publication.

Study data are analyzed as often as required to address regulatory queries, safety reporting requirements and clinical questions posed by investigators. In addition the study data are analyzed to support study research projects initiated and run by investigators in partnership with Pfizer.

In general, data from all patients with correct entered data will be analyzed at regular intervals. Protocol deviations will be listed per patient, describing the nature of the deviation as well as the times and reasons for discontinuation.

9.13. Analysis of safety

Safety outcomes of long-term Genotropin therapy are analyzed to provide information as requested. Frequency and incidence rates of AEs are calculated and compared to data on general populations, when available. Incidence and frequency rates of AEs are also compared between different subgroups in the study.

9.14. Quality control

The study will be monitored according to the monitoring plan.

As used in this protocol, the term case report form (CRF) should be understood to refer to an electronic data record.

A CRF should be completed for each included subject. The completed original CRFs are the sole property of Pfizer and should not be made available in any form to third parties, except for authorized representatives of Pfizer or appropriate regulatory authorities, without written permission from Pfizer.

The investigator has ultimate responsibility for the collection and reporting of all clinical, safety and laboratory data entered on the CRFs and any other data collection forms (source documents) and ensuring that they are accurate, authentic / original, attributable, complete, consistent, legible, timely (contemporaneous), enduring and available when required. The CRFs must be signed by the investigator or by an authorized staff member to attest that the data contained on the CRFs is true. Any corrections to entries made in the CRFs, source documents must be dated, initialed and explained (if necessary) and should not obscure the original entry.”

In most cases, the source documents are the hospital's or the physician's subject chart. In these cases data collected on the CRFs must match the data in those charts.

In some cases, the CRF, or part of the CRF, may also serve as source documents. In these cases, a document should be available at the investigator's site as well as at Pfizer and clearly identify those data that will be recorded in the CRF, and for which the CRF will stand as the source document.

9.15. Record Retention

To enable evaluations and/or audits from regulatory authorities or Pfizer, the investigator agrees to keep records, including the identity of all participating subjects (sufficient information to link records, e.g., CRFs and hospital records), all original signed informed consent forms, copies of all CRFs, serious adverse event forms, source documents, and detailed records of treatment disposition, and adequate documentation of relevant correspondence (e.g., letters, meeting minutes, telephone calls reports). The records should be retained by the investigator according to local regulations, or as specified in the Clinical Study Agreement, whichever is longer.

If the investigator becomes unable for any reason to continue to retain study records for the required period (e.g., retirement, relocation), Pfizer should be prospectively notified. The study records must be transferred to a designee acceptable to Pfizer, such as another investigator, another institution, or to an independent third party arranged by Pfizer. The investigator must obtain Pfizer's written permission before disposing of any records, even if retention requirements have been met.

9.16. Limitations of the research methods

In order to ensure a comprehensive view of the disease it is important that a majority of the treated patients can be included. Hence both patients with complicated disease as well patients with a less complicated disease should be included. Further is it important to ensure that the data from the different hospitals are qualitatively at a high standard and complete.

10. PROTECTION OF HUMAN SUBJECTS

10.1. Patient Information and Consent

All parties will ensure protection of patient personal data and will not include patient names on any sponsor forms, reports, publications, or in any other disclosures, except where required by laws. In case of data transfer, Pfizer will maintain high standards of confidentiality and protection of patient personal data.

The informed consent form must be in compliance with local regulatory requirements and legal requirements.

The informed consent form used in this study, and any changes made during the course of the study, must be prospectively approved by both the IRB/IEC and Pfizer before use.

The investigator must ensure that each study patient, or his/her legally acceptable representative, is fully informed about the nature and objectives of the study and possible risks associated with participation. The investigator, or a person designated by the investigator, will obtain written informed consent from each patient or the patient's legally acceptable representative before any study-specific activity is performed. The investigator will retain the original of each patient's signed consent form.

10.2. Patient withdrawal

Patients may withdraw from the study at any time at their own request, or they may be withdrawn at any time at the discretion of the investigator or sponsor for safety, behavioral, or administrative reasons. In any circumstance, every effort should be made to document patient outcome, if possible. The investigator should inquire about the reason for withdrawal and follow-up with the patient regarding any unresolved adverse events.

If the patient withdraws from the study, and also withdraws consent for disclosure of future information, no further evaluations should be performed, and no additional data should be collected. The sponsor may retain and continue to use any data collected before such withdrawal of consent.

10.3. Institutional Review Board (IRB)/Independent Ethics Committee (IEC)

It is the responsibility of the investigator to have prospective approval of the study protocol, protocol amendments, and informed consent forms, and other relevant documents, (e.g., recruitment advertisements), if applicable, from the IRB/IEC. All correspondence with the IRB/IEC should be retained in the Investigator File. Copies of IRB/IEC approvals should be forwarded to Pfizer.

10.4. Ethical Conduct of the Study

The study will be conducted in accordance with local legal and regulatory requirements, as well as with scientific purpose, value and rigor and follow generally accepted research practices.

11. MANAGEMENT AND REPORTING OF ADVERSE EVENTS/ADVERSE REACTIONS

11.1. Requirements

The table below summarizes the requirements for recording safety events on the SWEGHO e-CRF and for reporting safety events on the non-interventional study (NIS) adverse event monitoring (AEM) Report Form to Pfizer Safety. These requirements are delineated for three types of events: (1) serious adverse events (SAEs); (2) non-serious AEs (as applicable); and (3) scenarios involving drug exposure, including exposure during pregnancy, exposure during breast feeding, medication error, overdose, misuse, extravasation, and occupational exposure. These events are defined in the section "Definitions of safety events".

Safety event	Recorded on the SWEGHO e-CRF	Reported on the NIS AEM Report Form to Pfizer Safety within 24 hours of awareness
SAE	All	All
Non-serious AE	All	None
Scenarios involving exposure to a drug under study, including exposure during pregnancy, exposure during breast feeding, medication error, overdose, misuse, extravasation; lack of efficacy; and occupational exposure.	All (regardless of whether associated with an AE), except occupational exposure	All (regardless of whether associated with an AE)

For each AE, the investigator must pursue and obtain information adequate both to determine the outcome of the adverse event and to assess whether it meets the criteria for classification as a SAE (see section "Serious Adverse Events" below)

Safety events listed in the table above must be reported to Pfizer within 24 hours of awareness of the event by the investigator **regardless of whether the event is determined by the investigator to be related to a drug under study**. In particular, if the SAE is fatal or life-threatening, notification to Pfizer must be made immediately, irrespective of the extent of available event information. This timeframe also applies to additional new (follow-up) information on previously forwarded safety event reports. In the rare situation that the investigator does not become immediately aware of the occurrence of a safety event, the investigator must report the event within 24 hours after learning of it and document the time of his/her first awareness of the events.

For safety events that are considered serious or that are identified in the far right column of the table above that are reportable to Pfizer within 24 hours of awareness, the investigator is obligated to pursue and to provide any additional information to Pfizer in accordance with this 24-hour timeframe. In addition, an investigator may be requested by Pfizer to obtain specific follow-up information in an expedited fashion. This information is more detailed than that recorded on the

SWEGHO e-CRF. In general, this will include a description of the adverse event in sufficient detail to allow for a complete medical assessment of the case and independent determination of possible causality. Any information relevant to the event, such as concomitant medications and illnesses must be provided. In the case of a patient death, a summary of available autopsy findings must be submitted as soon as possible to Pfizer or its designated representative.

11.2. Reporting period

For each patient, the safety event reporting period begins at the time of the patient's first dose of Genotropin® or the time of the patient's informed consent if s/he is already exposed to Genotropin®, and lasts through the end of the observation period of the study, which must include at least 28 calendar days following the last administration of a drug under study; a report must be submitted to Pfizer Safety (or its designated representative) for any of the types of safety events listed in the table above occurring during this period. If a patient was administered a drug under study on the last day of the observation period, then the reporting period should be extended for 28 calendar days following the end of observation. Most often, the date of informed consent is the same as the date of enrollment. In some situations, there may be a lag between the dates of informed consent and enrollment. In these instances, if a patient provides informed consent but is never enrolled in the study (e.g., patient changes his/her mind about participation), the reporting period ends on the date of the decision to not enroll the patient.

If the investigator becomes aware of a SAE occurring at any time after completion of the study and s/he considers the SAE to be related to Genotropin®, the SAE also must be reported to Pfizer Safety.

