Patients are treated with GH over a long time period, usually over several years and for some patients the treatment duration can even be life-long, especially for the patients with CO-GHD. Due to the long treatment period it is of great value to continue the assessment further. In order to further strengthen the data previously collected in KIMS[®], this study is designed to further follow up long-term Genotropin therapy treatment outcomes in a real-world clinical setting and to be able to compare patients who started treatment after 2012 with patients who started treatment in 1990-ies. The Swedish KIMS[®] investigators have in their previous participation in KIMS[®] showed very high standard of execution and the data excellent quality. Therefore this NIS is particularly well suited to be continued in Sweden. The usefulness of Non-Interventional studies such as KIMS[®] can be exemplified by the article of Burman⁶ et al recently published in JCEM, where two important causes of excess mortality were identified in patients with hypopituitarism. Firstly, a lack of sufficient adrenal response to acute stress and intercurrent illness. Secondly, increased risk of a late appearance of de novo malignant brain tumors in patients who previously received radiotherapy. Both of these findings are important as they reflect preventable events in the management of pituitary disease.

The median follow-up period in KIMS[®] Sweden was approximately 9 years. One of the goals of this study is to prolong the long-term follow up of Genotropin therapy for patients included in KIMS[®]. It is anticipated that the study will prolong the median follow-up period with 3-5 years for the Swedish population. Another goal is to identify secular trends in Genotropin treatment regime and characteristics of treatment outcomes over 3 decades of GH replacement in adult patients with GHD. Patients are to be enrolled, treated and followed at the discretion of the investigator (the treating physician), who will collect and enter patient data into electronic case report forms (eCRFs). This non-interventional study does not include a pre-specified hypothesis.

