9.8. Variables

The variables to be captured are listed in **Table 1**.

Table 1. Variables to be captured (if available).

Variable	Role*	Data source(s)
Informed Consent (mandatory)	Before Baseline	Personally signed and dated Informed Consent Document
BACKGROUND INFORMATION -Age -Gender - Ethnic origin -Age at menarche -Menopause/Amenorrea -Age at Menopause/Amenorrea -Puberty (Induced, Spontaneous) -Age at end of growth	Baseline	Patient record and or CRF
MEDICAL HISTORY -Hypertension -Claudication -Coronary Heart Disease -Stroke -Arthrosis -Diabetes -Type I -Type II -Epilepsy -Neoplasm -Other Significant disease -Fractures	Baseline	Patient record and or CRF
FAMILY HISTORY -Diabetes -Cardiovascular Disease	Baseline	Patient record and or CRF

-Hip Fracture -Colon Polyps -Colon Cancer -Neoplasm (other)		
PITUITARY DISEASE -Date of Diagnose -Childhood onset -Brain Tumor -Visual Field deficit -Ophthalmoplegia -Tumor treatment -Tumor Size -Tumor type	Baseline	Patient record and or CRF
DIAGNOSE OF GHD -Date of Diagnose of GHD -Test method -Date of test	Baseline	Patient record and or CRF
BASELINE PREVIOUS GH TREATMENT -Treatment start date -Treatment stop date	Baseline	Patient record and or CRF
EXAMINATION -Age -Weight -Height -Blood pressure -CT/MRI -Body Composition -Additional Hormone Abnormalities	Baseline, Follow up visit	Patient record
TREATMENT -GH treatment -Concomitant Medication of special interest	Baseline, Follow up visit	Patient record
LABORATORY -Glucose -HbA1c -IGF-I	Baseline, Follow up visit	Patient record
ADVERSE EVENT	Follow up visit	Patient record and information obtained from the patient

Detailed operational definitions will be included in the Statistical Analysis Plan.

*For patients previously treated in KIMS[®] historical data will automatically inserted into the Database.

Concomitant Medication of Special Interest:

It is recommended to collect all concomitant medication. The particular attention should be given to the following concomitant medication of special interest:

1. Replacement of other pituitary hormone deficits: sex steroids, glucocorticoids, thyroxine and vasopressin
2. Treatment of prolactin abnormalities
3. Antihypertensive drugs
4. Lipid lowering drugs
5. Anti-diabetic drugs
6. Antidepressant drugs
7. Anti-epileptic drugs

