#### 4 ENDPOINTS AND COVARIATES

The patient is treated according to clinical practice. Normal clinical practice may include routine diagnostic procedures such as; blood samples, CTs, MRI and other tests. The decision of what measures to perform is not pre-specified in the protocol but is based on the clinical experience, standards and judgment of the investigator. Data from patient records, which align with the data to be collected in the database eCRF as specified in the study protocol, is collected and entered into the database. The data is collected during the patients' routine visits to the clinic.

Endpoints will be summarized at baseline and at follow up and change from baseline will be derived if appropriate.

Continuous data will be summarized using descriptive statistics where the following parameters will be reported:

- Number of observations (n),
- Mean,
- Quartile 1 (Q1),
- Median,
- Quartile 3 (Q3),
- Standard deviation (SD),
- Range (Min,Max)

Categorical data will be presented as the number and percentage of patients.

In general, all data will be listed. Summary tables will be structured with a column for each of the three subgroups defined in Section 3.3 and a column for the total if other not stated.

The following variables should be captured according to the Study Protocol (if available):

Variable	Role	Data source(s)	
Informed Consent (mandatory)	Before Baseline	Personally signed and dated Informed Consent Document	
BACKGROUND INFORMATION -Age -Gender - Ethnic origin (only CRF) -Age at menarche	Baseline		

-Menopause/Amenorre -Age at Menopause/Amenorrea -Puberty (Induced, Spontaneous) -Age at end of growth			
MEDICAL HISTORY -Hypertension -Claudication -Coronary Heart Disease -Stroke -Arthrosis -Diabetes -Type I -Type II -Epilepsy -Neoplasm -Other Significant disease -Fractures	Baseline	Patient record and or CRF	
FAMILY HISTORY -Diabetes -Cardiovascular Disease -Hip Fracture -Colon Polyps -Colon Cancer -Neoplasm (other)	Baseline	Patient record and or CRF	
PITUITARY DISEASE -Date of Diagnose -Childhood onset -Brain Tumor -Visual Field deficit -Ophthalmoplegia -Tumor treatment -Tumor Size -Tumor type	Baseline	Patient record and or CRF	
DIAGNOSE OF GHD -Date of Diagnose of GHD -Test method -Date of test	Baseline	Patient record and or CRF	
BASELINE PREVIOUS GH TREATMENT -Treatment start date -Treatment stop date	Baseline	Patient record and or CRF	

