## 4.3 SAFETY ENDPOINTS

For each patient, the safety event reporting period begins at the time of the patient’s first dose of Genotropin® or the time of the patient’s informed consent if s/he is already exposed to Genotropin®, and lasts through the end of the observation period of the study, which must include at least 28 calendar days following the last administration of a drug under study. Most often, the date of informed consent is the same as the date of enrollment. In some situations, there may be a lag between the dates of informed consent and enrollment. In these instances, if a patient provides informed consent but is never enrolled in the study (e.g., patient changes his/her mind about participation), the reporting period ends on the date of the decision to not enroll the patient.

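### The AE comparison between subgroups does not align time on Genotropin: KIMS patients enter after years of treatment, new starters from the first dose

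*Protocol*

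**What the plan says.** **Window.** Protocol 11.2 starts AE reporting at the patient's "first dose of Genotropin® or the time of the patient's informed consent if s/he is already exposed" to the drug. The window then "lasts through the end of the observation period of the study, which must include at least 28 calendar days" after the last administration. SAP 4.3 repeats the two starting points: "the safety event reporting period begins at the time of the" first dose, or at "informed consent if s/he is already exposed to Genotropin".

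**Comparison.** Protocol 9.13 states: "Incidence and frequency rates of AEs are also compared between different subgroups in the study". SAP 4 adds: "Summary tables will be structured with a column for each of the three subgroups defined in Section 3.3", plus a total. SAP 3.3 defines the columns as CO-GHD (any childhood-onset patient), K-AO-GHD (diagnosed before 2013, previously treated with Genotropin and followed in KIMS) and N-AO-GHD (newly diagnosed).

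**Entry.** Inclusion criterion 2 (Protocol 9.3) requires a current Genotropin prescription. Criterion 1a sets no limit on the time between starting Genotropin and consent. Protocol 7 says that the median follow-up in KIMS "Sweden was approximately 9 years".

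**Adjustment.** SAP 4.5 and 6.2 plan descriptive summaries only, without covariates. The one duration defined (SAP 4.4) runs from the SWEGHO baseline. SAP 4.3.1 defines no person-time for AEs. The caution in SAP 6.1 concerns only the missing comparator arm.

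**Available data.** Protocol Table 1 lists "Treatment start date -Treatment stop date" for previous GH treatment, to be captured if available.

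**The concern.** The subgroups differ by construction in the part of the treatment course that SWEGHO observes. K-AO-GHD patients are prevalent users: they were treated earlier, and anyone who had stopped for good before consent, whether for intolerance or another reason, cannot enter. N-AO-GHD patients who start at entry are seen from the first dose. Those who started before consent are seen only from consent, and their number is not stated. The CO-GHD column can hold both kinds of patient. This is left truncation, and dividing by person-time does not remove it, because the person-time comes from different phases of treatment.

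If AE risk changes with time on treatment, the columns will differ even when patients at the same time since first dose have the same risk. A higher rate in N-AO-GHD could be read as worse safety in today's patients. A low rate in K-AO-GHD could be read as good long-term safety when it partly reflects who was still on the drug. The temptation is real, because comparing patients included from 2013 with those treated from the 1990s is a stated purpose of the study (Protocol 8).

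**Working it through.** **1. The plan's own figure.** Protocol 9.10 expects 600 KIMS + 250 new + 50 childhood-onset = 900 patients, which matches its stated total. The SAP reports around 340 included at version 1.0, without a split by subgroup. Neither document gives an AE rate, so the size below is an illustration.

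**2. First-year time in K-AO-GHD.** KIMS ran to 2012 and SWEGHO data collection was planned to start on 30 October 2013. A patient first treated at the very end of 2012 and enrolled on the first day is already about 10 months past first dose. First-year time in this column is therefore close to zero.

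**3. First-year share s in new starters.** Let F be follow-up from first dose, with a study of 5 years. Then s = E[min(F,1)] / E[F].

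- All enter at the start (F = 5): s = 1/5 = 0.20.
- Entry uniform over 5 years (F uniform on 0 to 5): E[min(F,1)] = 0.1 + 0.8 = 0.9 and E[F] = 2.5, so s = 0.9/2.5 = 0.36.
- With an assumed dropout rate of 20% per year, these shares become 0.287 and 0.445.

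**4. Crude rate ratio with no true difference.** Let the AE rate be λ after year 1 and rλ in year 1, the same function of time since first dose in both groups. K-AO-GHD then has rate λ. New starters have s·rλ + (1 − s)λ. The crude ratio of N-AO-GHD to K-AO-GHD is 1 + s(r − 1).

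| r (assumed) | s = 0.20 | s = 0.36 |
|---|---|---|
| 0.5 | 0.90 | 0.82 |
| 1.0 | 1.00 | 1.00 |
| 1.5 | 1.10 | 1.18 |
| 2 | 1.20 | 1.36 |
| 3 | 1.40 | 1.72 |

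**5. Some new patients already exposed at consent.** If only half of them take their first dose inside the window and the others contribute no first-year time, s is halved. At r = 2 the ratio is 1 + 0.5 × 0.20 = 1.10 to 1 + 0.5 × 0.36 = 1.18.

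**6. After banding by time since first dose.** Under the same assumptions the ratio within a shared band is 1. The first-year band has almost no K-AO-GHD time to compare with.

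**The case against.** - **The reporting rule is not the cause.** A reader might infer from the two starting points that Protocol 11.2 creates the contrast. It does not. For a patient who starts at entry, first dose and consent roughly coincide, so opening every window at consent would change little. The imbalance comes from putting prevalent and new users side by side. This stands.
- **It is not first-year against late treatment.** A reader might also infer this stronger contrast. The new-starter window runs to the end of observation, and 64% to 80% of that person-time lies after year 1 (1 − 0.36 and 1 − 0.20). This stands.
- **The comparison may be of something else.** Protocol 9.13 does not name the SAP 3.3 groups, and Protocol 9.6 calls the diagnosis code one of the most important grouping variables. The SAP specifies no AE rate and no hypothesis test, and its table shells are in a separate TLF plan that may contain exposure-time tables. This limits the harm to a misleading descriptive contrast. It does not remove it: the SAP 3.3 groups are the only subgroups the SAP defines and are its default columns.
- **KIMS data are transferred.** They could in principle supply early-treatment events, but neither document says how they would enter the AE analysis.
- **Size and direction are assumed.** AEs are counted whatever their cause, and Protocol 7 itself describes late malignant brain tumours after radiotherapy. For such events r could be below 1. This stands.
- **The 9-year median is not a bias estimate.** One could compute 9/(9 + 5) = 64% of a typical KIMS patient's observed treatment time as lying before the window. But that median describes Swedish KIMS as a whole, not those who re-enrol, and time outside the window causes no bias if the rate is constant.

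**Conclusion.** The point holds as a prevalent-user problem in the subgroup comparison of AEs. The plan compares groups observed at different times since first dose, selects all of them on still being prescribed the drug, and neither aligns nor adjusts for this. A crude difference cannot separate patient group from treatment phase.

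The illustrated size is modest to moderate: a crude ratio of 1.10 to 1.18 at r = 1.5 and 1.20 to 1.36 at r = 2, smaller if some new patients started before consent. It rests on assumed values of r, flat risk after year 1, the entry pattern and, in the main range, no dropout. It disappears at r = 1 and reverses below 1. The documents do not support a firm direction, a false test result (no tests are planned) or a fault in the reporting-period rule. The change is worth making because it is cheap and the comparison is otherwise hard to interpret.

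**What to change.** Keep the collection window as it is. In SAP 4.3:

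1. Report AE and SAE rates per person-time by time since first-ever Genotropin dose, where the start date is recorded (for example under 1, 1 to under 5, 5 to under 10, and 10 or more years). Each patient enters at the later of first dose and consent.
2. Compare subgroups only within bands where both have person-time.
3. State that the unbanded subgroup columns are descriptive and not comparable for safety.
4. State that SWEGHO-window data support no conclusion about early-treatment AEs in K-AO-GHD.

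The cost is SAP wording and one more set of AE tables. No new variables are needed: Table 1 already lists previous GH treatment dates and current GH treatment. The SAP must say how the first Genotropin dose is derived from them, since the variable is headed as GH treatment in general.

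The downsides are real. Cells will be small. Many bands will show little or no overlap between N-AO-GHD and K-AO-GHD: those of 5 years or more hold almost no new-starter time, and below that the overlap depends on how many patients joined KIMS late. Patients without a recorded start date drop out of the banded tables and should be counted.
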